Preoperative antibiotic usage will be standardized (as per SCIP protocol) as follows. All patients will receive a second generation cephalosporin within 60 minutes prior to the surgical incisions. Patients with a prior history of penicillin allergy or MRSA wound/mesh infections will instead receive a preoperative dose of intravenous vancomycin. The exact drug, along with the dose, frequency, and time administered will be recorded. All antibiotics will be discontinued after 24 hours of surgery unless otherwise indicated. Prolonged antibiotic usage will be clearly documented as to indication, type, dose, frequency, and duration.

The surgical approach to repairing these defects will be standardized, as previously described. All patients will receive a chlorhexidine skin preparation, an iodine-impregnated skin barrier, and all stoma sites will be over sewn at the muco-cutaneous junction to limit bacterial contamination prior to skin preparation. If patients have an allergy to chlorhexidine, then Duraprep™ will be utilized. For any patient who has an allergy to iodine, then a Steri-Drape may be used as a skin barrier. Hair will be removed at the time of surgery with electric clippers. The midline fascia will be opened and complete adhesiolysis performed to free up the entire abdominal wall. All concomitant procedures will be performed prior

to beginning the abdominal wall reconstructive phase, and documented.

Intraoperative concomitant procedures will be allowed unless they change the wound classification to a class 4. Acceptable concomitant procedures include: the creation of a stoma, bowel resection, gastrointestinal surgery, genitourinary surgery, gynecological surgery, panniculectomy, and removing uninfected mesh.

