## Class 2: Clean-Contaminated

Operative wounds in which the respiratory, alimentary, genital\*, or urinary tract are entered under controlled conditions, and without unusual contamination. Specifically, operations involving the biliary tract, appendix, vagina, and oropharynx are included in this category, provided no evidence of infection or major break in technique is encountered.

\*Includes female and male reproductive tracts

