## Class 3- Contaminated

A surgical field with any of the following: open, fresh, accidental wounds; operations with major breaks in sterile technique or gross spillage from the gastrointestinal tract; and incisions in which acute, nonpurulent inflammation is encountered.

Following wound classification, the allocation of the patient to either the biologic mesh cohort or the permanent synthetic mesh cohort will be revealed to the operating surgeon, according to the previously-described computer-generated block randomization scheme stratified by wound classification and medical center. The corresponding prosthetic material will then be placed with at least 5

cm of fascial coverage on all sides of the defect. The mesh will be fixated with trans-abdominal #1 Maxon or PDS sutures at 5-10 cm intervals. Number of sutures to secure the mesh will be documented. All patients will have closed suction drains placed above the mesh and below the fascial closure. These drains will be removed postoperatively when the collected fluid is < 30 cc/day for 48 hours and documented. The fascia will be closed with a running or interrupted Maxon or PDS #1 suture. The skin will be closed loosely with staples. Dry sterile dressings will be placed at the conclusion of the procedure and will be removed on postoperative day 2. No further dressings will be applied to the wound.

Postoperative complications will be defined and recorded on the CRF's based on CDC standardized terms and definitions for Surgical Site Infections as follow: [42, 43]-See appendix 4.

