The first task to address this specific aim will be to estimate direct and indirect economic costs associated with clean-contaminated and contaminated open ventral hernia repair. A micro-costing approach will be used assuming a limited societal perspective. Costs associated with the preoperative, operative, and postoperative phases of care will be considered as it pertains to the management of the ventral hernia. In most cases, one to two preoperative clinic visits will be necessary. Final operative costs will be based on each patient's actual inpatient encounter cost obtained from the participating institutions. Postoperative costs

will account for routine outpatient visits, costs incurred for complications, and time lost from work due to ventral hernia management. All costs will be reported in U.S. dollars, adjusted for the years in which the data were obtained. Should institutional data not be available for a particular cost, the best available evidence from currently published analyses will be used. The second task for this specific aim is to perform health utility valuation in patients undergoing open repairs of clean-contaminated and contaminated ventral hernias. Patients will be administered the EQ-5D and the HerQLes instruments at one preoperative visit and postoperatively at scheduled visits at 4 weeks ( $\pm 2$  weeks), 6 months ( $\pm 2$  month), and 12 months ( $\pm 3$  months), and 24 months ( $\pm 4$  months). HerQLes and EQ-5D valuations will be converted to health utility estimates based on published norms from the Agency for Healthcare Research and Quality (AHRQ). Quality-adjusted life years (QALYs) will be calculated based on these health utilities obtained in the postoperative phase. For a given strategy (light-weight macroporous polypropylene mesh or biologic mesh), it is anticipated that health utility variation will be affected more than survival. As such, calculations of QALYs will assume that all patients survive during the 24 month follow-up period, but differ in their health utility valuation.

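### Aim 2 bases operative cost on the inpatient encounter with no rule for concomitant surgery; a prespecified adjustment would sharpen the cost comparison cheaply

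*Combined protocol and SAP*

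**What the plan says.** The costing rules are in the Specific Aim 2 text of the Analysis section. The scope is "Costs associated with the preoperative, operative, and postoperative phases of care will be considered as it pertains to the management of the ventral hernia". The method is "A micro-costing approach will be used assuming a limited societal perspective". The operative component is then defined: "Final operative costs will be based on each patient's actual inpatient encounter cost obtained from the participating institutions".

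Study Procedures lists what may be done at the same operation: "Acceptable concomitant procedures include: the creation of a stoma, bowel resection, gastrointestinal surgery, genitourinary surgery, gynecological surgery, panniculectomy, and removing uninfected mesh". Clean-contaminated wounds are defined by tract entry (Class 2 definition): "Operative wounds in which the respiratory, alimentary, genital\*, or urinary tract are entered under controlled conditions".

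Two further provisions matter for the remedy. On timing, Study Procedures says "All concomitant procedures will be performed prior" to the start of the reconstruction, and the text after the Class 3 definition adds: "Following wound classification, the allocation of the patient to either the biologic mesh cohort or the permanent synthetic mesh cohort will be revealed". On data, concomitant procedures are among the intraoperative details to be recorded.

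Cost-Effectiveness Evaluation then calls for costs, QALYs, plain cost-effectiveness ratios and incremental ratios, to be fed through a decision model with sensitivity analyses.

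**The concern.** The scope sentence and the operative-cost sentence do not obviously describe the same quantity. In a clean-wound hernia trial the encounter and the hernia repair would be nearly the same thing. Here the population is defined by contamination, which often arises because another organ is operated on, so the encounter can carry substantial cost that has nothing to do with the choice of mesh. No Aim 2 text apportions that cost or adjusts for it.

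The adjustments found elsewhere do not reach it. The imbalance rule under Primary Analyses of Primary Outcomes concerns demographic and preoperative characteristics. The prespecified Cox models concern recurrence and wound healing. The center terms are described for the Aim 1 analyses. Randomization is stratified by center and wound class, not by procedure.

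Two things are at stake: what the per-strategy cost figures mean, and how precisely the cost difference between meshes is estimated.

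**Working it through.** **No figure to reproduce.** The plan states no mean, SD, power or interval for cost. Every dollar figure below except the mesh prices is an assumption.

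**Inputs from the documents**
- Enrolled: 253, so about 126 per arm (253 / 2 = 126.5).
- Evaluable after 20% loss to follow-up: 253 × 0.80 = 202, or 101 per arm (Power Calculation).
- List prices: over $10,000 for a 400 cm² biologic graft and about $150 for a 900 cm² synthetic mesh (Specific Aims). The gap is about $10,000 − $150 = $9,850. The sizes differ, so this is only a yardstick.

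**Assumed inputs**
- SD of encounter cost: $15,000 to $30,000.
- Share of patients with a given added procedure: q = 0.5.
- Cost that it adds: C = $10,000 to $20,000.

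**Step 1: level.** If the hernia-only encounter costs H, an encounter with added surgery is higher by C/H and the arm mean by qC/H. For wider assumed ranges, C of $5,000 to $20,000 and H of $20,000 to $40,000:
- C/H runs from 5,000/40,000 = 12.5% to 20,000/20,000 = 100%.
- With q = 0.5, the arm mean is raised by about 6% to 50%.

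**Step 2: difference.** Procedures are finished before the surgeon learns the allocation, so qC is expected equally in both arms: (H + 9,850 + qC) − (H + qC) = 9,850. The expected incremental cost does not change.

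**Step 3: precision.** The variance due to the procedure is q(1 − q)C² = 0.25C². Its share of total variance is R² = 0.25C²/SD². Adjustment multiplies the interval width by √(1 − R²).

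| SD | C | 0.25C² (millions) | SD² (millions) | R² | Narrowing |
|---|---|---|---|---|---|
| $15,000 | $10,000 | 25 | 225 | 11.1% | 5.7% |
| $15,000 | $20,000 | 100 | 225 | 44.4% | 25.5% |
| $30,000 | $10,000 | 25 | 900 | 2.8% | 1.4% |
| $30,000 | $20,000 | 100 | 900 | 11.1% | 5.7% |

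The range is about 1% to 25%.

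**Step 4: dollars.** The 95% half-width is 1.96 × SD × √(2/n).
- n = 126 per arm: $3,704 (SD $15,000) and $7,408 (SD $30,000).
- n = 101 per arm: $4,137 and $8,274.

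Inpatient cost is fixed at discharge, so later loss to follow-up need not reduce the sample, and 126 is the more natural n. After adjustment at n = 126, $3,704 becomes $3,492 (C = $10,000) or $2,761 (C = $20,000), and $7,408 becomes $7,304 or $6,984.

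**Step 5: chance imbalance.** At 101 per arm the SD of the imbalance in a 50% procedure is √(2 × 0.25/101) = 0.070. Multiplied by C, that is $704 to $1,407. It is already contained in the total standard error of $2,111 to $4,222 (SD × √(2/101)), so it is not a further harm to add on.

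**The case against.** The case against is substantial, and most of it stands.

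- A reader might infer that the plan does overstate the cost of hernia repair. The documents do not establish this. Operative cost is only said to be based on the encounter, under micro-costing and a hernia-related scope, and none of this rules out apportionment. What is shown is a missing rule and two sentences that are not reconciled.
- Whole-encounter cost is a defensible unit. Aim 2 costs clean-contaminated and contaminated repair, and the contamination is part of the population.
- Tract entry is not the same as separate surgery. The rationale for the synthetic mesh mentions parastomal repair and inadvertent enterotomy, and removal of uninfected mesh is itself listed as concomitant. Such costs may belong to the hernia repair. The documents give no frequency for any procedure, so one cannot say that most encounters carry unrelated cost.
- A reader might also infer that the mesh comparison is biased. It is not, in expectation: randomization and the late reveal put the same expected procedure cost in both arms, and an unadjusted comparison is valid.
- The plan specifies no test or interval for the cost difference. Stratification by center and wound class may already limit some of the imbalance.

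What survives is narrower. Randomization does not cancel other surgery out of per-strategy costs or plain ratios, both of which the plan reports. Nor does it remove procedure-related variance from the incremental cost, whose uncertainty matters to the decision model even without a formal test.

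**Conclusion.** The point holds as a minor one. Unless encounter cost is apportioned, the cost and plain cost-effectiveness ratio of each strategy would include concomitant surgery, while the stated scope is the hernia. The incremental cost is unbiased in expectation but less precise than the recorded data allow. The size of the gain cannot be derived from the documents. Under the assumptions above it is a narrowing of about 1% to 25%, and three of the four combinations give 6% or less. More procedure categories could explain more variance, but nothing in the documents shows that they would.

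It would be tempting to cite the full half-width of several thousand dollars against the $9,850 price gap as the harm. That figure is the total imprecision of the cost comparison, not the part due to this issue. The primary clinical outcomes are unaffected.

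**What to change.** Keep the encounter cost as the operative cost, and add the following to the Aim 2 analysis:

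1. Estimate the incremental cost from a prespecified regression of cost on mesh, center, final wound class and concomitant-procedure category. Code the categories from what was done before the allocation was revealed to the surgeon, so that adjustment cannot remove any effect of the mesh.
2. Carry the adjusted difference into the model in Cost-Effectiveness Evaluation, and report the unadjusted difference alongside.
3. Label absolute costs and plain ratios as encounter cost including concomitant surgery, and align the scope sentence with that label.

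Do not strip out concomitant cost lines by default. Some, such as removal of uninfected mesh, may belong to the hernia repair, and bed-days are shared between procedures, so removal could understate hernia cost.

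The cost is a few lines of analysis-plan text and one regression on variables already collected. The downside is that the procedure categories must be defined before unblinding. The analysts stay blinded until the study ends, so there is time to do this.

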CT scan as clinically indicated. Preoperative demographics and clinical data including sex, race, age, body mass index (BMI), location of the hernia, length and width of the hernia defect, wound classification(per CDC guidelines, table 1), smoking status (active within 3 month of surgery), medical history, surgical history of prior abdominal surgical procedures and prior ventral/incisional hernia repairs will be documented. Intraoperative details will include patient ASA score, patient temperature, use of epidural catheters, size of fascial defect (measured as maximal width and length), fascial layers released (external oblique, posterior rectus sheath, or transversus abdominis muscle), adhesions, concomitant procedures, wound characterization, mesh type, mesh placement, operative time, estimated blood loss, blood transfusion requirement, perioperative antibiotic administration (including type, dose, frequency, and times of initiation and discontinuation), and intraoperative fluid administration. Postoperatively, patients will be evaluated for signs and symptoms of complications along with presence or absence of surgical site infections (SSIs) per CDC definitions as categorized below (Appendix 4), presence or absence of surgical site occurrences (SSOs) and any procedural interventions required to treat these SSOs, presence or absence of hernia recurrence and any reoperations, length of hospital stay, discharge date, time to return of bowel function and any readmission. Wound erythema treated with antibiotics will be considered a wound cellulitis. Wounds that are opened and cultured will be appropriately categorized as postoperative SSIs based on CDC definitions. Type, dose, frequency, and duration of antibiotics will be recorded. Patients will also fill out HerQLes (Appendix 1) and

EQ-5D (Appendix 2) quality of life tools preoperatively and during each post-operative visit, at 4 weeks (± 2 weeks), 6 months (± 2 month), 12 months (± 3 months), and 24 months (± 4 months). See Appendix 7 for Plan for Continuation of Study Follow-up Visits for Patients Previously Enrolled at University Hospital. There is substantial evidence that the majority of hernia recurrences occur within the first 24 months after repair.[5, 15, 41]

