### *Power Calculation*

33

Version date 4/17/19

CCF #7

NCT02451176

We are investigating two primary outcomes: surgical site occurrences requiring procedural intervention (SSOPI) and hernia recurrence (HR). Surgical site occurrences requiring procedural intervention (SSOPI) is a repeated binary outcome measurement. Hernia recurrence (HR) is a single binary outcome measurement. In a multi-institutional retrospective review of clean-contaminated and contaminated ventral hernia repair, hernia recurrence rates were 29.21% versus 9.01%, and surgical site occurrences requiring procedural intervention were 39.02% versus 9.01% for the biological mesh and permanent synthetic mesh cohorts, respectively.[44] Based on review of these multi-institutional data, an estimated 253 patients will be enrolled in the proposed trial. Assuming a maximum 20% loss to follow-up, 202 patients will remain in the study sample for a 1:1 randomized allocation to each treatment arm (101 subjects per cohort). At the two-tailed overall (two hypotheses) type I error rate of 0.05, the study will have 92% power to detect a significant difference in the rates of hernia recurrence (29.21% vs. 9.01%), and a 100% power to detect a significant difference in surgical site occurrences requiring surgical intervention for the primary hypothesis (39.02% vs. 9.01%; with four repeated measurements and autoregressive correlation of  $\rho=0.5$ ) With 4 centers each performing approximately 1 eligible procedures per week, there will be 192 total procedures performed per year, from which it would be feasible to achieve the total enrollment goal of 253 subjects within 2 years.

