### **Analyses of Secondary Outcomes:**

The secondary outcomes are pain and quality of life (QOL). The assessment of the association between these outcomes and mesh type will parallel what was described above for the primary outcome. The differences are as follows. First, the primary analysis will utilize an ANCOVA model adjusting for baseline pain (QOL) and correlations among repeated measurements. The null hypothesis is that the pain (QOL) is the same, on average, between the synthetic and biologic mesh groups (H0: Beta-mesh-type = 0). The alternative hypothesis is that the pain (QOL) is different, on average, between the two groups (H1: Beta-mesh-type not= 0). Second, the multivariable modeling will utilize multiple linear regressions. A mixed model analysis with repeated measures will be performed to determine if a significant difference exists between the biologic mesh and the permanent synthetic mesh cohorts in the mean change in score from the preoperative assessment to the postoperative assessments at 1 month, 6 months, 12 months, and 24 months for the EQ-5D and HerQLes quality of life instruments. The null hypothesis is that there is no significant difference between the biologic mesh and the permanent synthetic mesh cohorts in the mean change in score from the preoperative to the postoperative assessments at any of the time points for either the EQ-5D or the HerQLes quality of life instruments. The alternate hypothesis is that there is a significantly greater change in EQ-5D

and HerQLes scores from the preoperative assessment to the postoperative assessment at each of the time points for the permanent synthetic mesh cohort compared to the biologic mesh cohort

In these data analyses, we will explore the possibility of medical center effect and treatment by medical center interaction. In particular, in the regression analyses, we will use indicator variables for medical center effect and indicator variable\*treatment for possible treatment by medical center interaction. If treatment by medical center interaction is significant, then it is more appropriate that the treatment effects are summarized by medical center.

**Specific Aim 2 - Demonstrate that a macroporous light-weight polypropylene mesh is the more cost-effective strategy than a biologic prosthetic in clean-contaminated and contaminated abdominal wall reconstruction.**

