### *Cost-Effectiveness Evaluation*

Once costs and QALYs have been calculated for each strategy, a decision analysis model will be constructed incorporating these values and the associated outcomes and complications that are thought to have an impact on which

strategy is the better choice for patients. One-way and two-way sensitivity analyses will be performed to help determine the degree to which each variable impacts the decision to choose either a light-weight macroporous polypropylene mesh or biologic mesh for repair of clean-contaminated or contaminated ventral hernias. If appropriate, a multi-way probabilistic sensitivity analysis will be performed incorporating the uncertainty associated with known values for certain variables. Costs, effectiveness (as measured by QALYs), cost-effectiveness ratios, and incremental cost-effectiveness ratios will be calculated to help determine the best strategy for mesh selection based on the results from this study and published data.

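### QALYs treat every patient as alive for 24 months and use only postoperative utilities, so deaths earn utility for time not lived and the preoperative EQ-5D has no part in the QALY

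*Combined protocol and SAP*

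**What the plan says.** The text on Specific Aim 2 in the Analysis section of the combined protocol and SAP sets two rules for the QALY.

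- Survival: "calculations of QALYs will assume that all patients survive during the 24 month follow-up period". The reason offered is that utility is expected to be affected more than survival.
- Utilities: "Quality-adjusted life years (QALYs) will be calculated based on these health utilities obtained in the postoperative phase".

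The same text provides for a baseline measurement: "Patients will be administered the EQ-5D and the HerQLes instruments at one preoperative visit", followed by visits at 4 weeks and 6, 12 and 24 months. Under Analyses of Secondary Outcomes, the Aim 1 comparison of pain and quality of life is an ANCOVA that adjusts for the baseline score. Nothing extends that adjustment to QALYs.

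Under Cost-Effectiveness Evaluation: "Once costs and QALYs have been calculated for each strategy, a decision analysis model will be constructed incorporating these values". The outputs are listed as follows: "Costs, effectiveness (as measured by QALYs), cost-effectiveness ratios, and incremental cost-effectiveness ratios will be calculated". One-way and two-way sensitivity analyses are planned, with a probabilistic analysis if appropriate. Neither survival nor baseline utility is named as an input to vary.

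**The concern.** A QALY combines length and quality of life. The survival rule fixes length at 24 months for everyone, which is false for any patient who dies, and the plan does not say what utility is credited after death. An expectation that utility will vary more than survival does not make deaths equal between arms in number or timing.

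Cost-effectiveness is one of the trial's two specific aims, and QALYs are the only effectiveness measure named for its ratios. Each arm's own cost-effectiveness ratio is to be reported. Over-crediting flatters that ratio even when deaths are balanced. The incremental QALY is distorted when the number or timing of deaths, or the utility credited, differs by arm, and the error then favours the arm that did worse on survival.

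The baseline omission is a separate and milder matter. Under randomisation, baseline differences arise by chance, so ignoring them adds variance and not bias. It does sit oddly beside the baseline-adjusted Aim 1 analysis. The interval from surgery to 4 weeks also has no starting value, which is minor.

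**Working it through.** The plan states no QALY, utility or mortality figure, so there is nothing of its own to reproduce. The only input taken from the documents, apart from the visit times, is 101 evaluable patients per arm (Power Calculation). Everything else is an assumption.

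**Over-credit from deaths.** Error in an arm's mean QALY per death = utility × years not lived ÷ 101.

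- Central: 0.7 × 1.0 / 101 = 0.0069
- Low: 0.5 × 0.5 / 101 = 0.0025
- High: 0.9 × 1.5 / 101 = 0.0134

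For an arm's own mean, at 1% mortality the excess is 0.01 × 0.7 = 0.007, or 0.01/1.99 = 0.5%. At 5% it is 0.05 × 0.7 = 0.035, or 0.05/1.95 = 2.6%.

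For the increment, error = difference in death proportion × utility × (24 − month of death)/12. With utility 0.7 to 0.8 and death at month 12 to month 1:

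- 1-point difference: 0.01 × 0.7 × 12/12 = 0.007 up to 0.01 × 0.8 × 23/12 = 0.015
- 5-point difference: 0.05 × 0.7 × 12/12 = 0.035 up to 0.05 × 0.8 × 23/12 = 0.077
- Equal deaths, timing and credited utility: 0

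**Precision lost by ignoring baseline.** Assume utility SD 0.2 at every visit and equal correlation r between visits. The trapezoid weights in years at preoperative, 4 weeks, 6, 12 and 24 months are 0.038, 0.250, 0.462, 0.750 and 0.500 (sum 2.0). The postoperative-only version moves 0.038 to the 4-week value.

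- Var(QALY) = 0.2² × [(1 − r)Σw² + r × 2²]
- Planned SE of the difference = √(2 × Var / 101), using the postoperative-only weights
- Adjusted SE = √(2 × Var × (1 − ρ²) / 101), using the full weights, where ρ is the correlation of baseline utility with the area under the curve

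**Cost of counting deaths.** If mesh does not affect survival, chance differences in deaths add SE = 0.7 × √(2m(1 − m)/101) at mortality m. This is 0.7 × 0.0140 = 0.0098 at 1% and 0.7 × 0.0307 = 0.0215 at 5%. Net SE adds the variances, taking death as independent of utility.

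| r | Planned SE | ρ | Adjusted SE | Net SE, 1% mortality | Net SE, 5% mortality |
|---|---|---|---|---|---|
| 0.3 | 0.0396 | 0.447 | 0.0353 | 0.037 | 0.0413 |
| 0.5 | 0.0450 | 0.639 | 0.0345 | 0.036 | 0.0407 |
| 0.7 | 0.0498 | 0.798 | 0.0300 | 0.032 | 0.0369 |

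At 5% mortality the full fix is slightly less precise than the plan at r = 0.3 and more precise at 0.5 and 0.7. At 1% it is more precise at all three.

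**A chance baseline imbalance.** If an imbalance of 0.05 carries into follow-up with an assumed coefficient of 0.3 to 0.7, the unadjusted two-year difference shifts by 2 × 0.05 × 0.3 = 0.03 to 2 × 0.05 × 0.7 = 0.07.

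**Missing start value.** An error of 0.1 in the starting utility gives 0.1 × (28/365.25)/2 = 0.004 QALY.

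**The case against.** The survival assumption is disclosed and given a reason, so it is a simplification and not a contradiction. Nothing in the documents suggests that mesh type affects survival, and equal deaths leave the increment untouched. That stands, and it limits the likely size of the error.

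The effect may also be too small to change the decision. The protocol prices a 400 cm² biologic graft at over $10,000 and a 900 cm² synthetic mesh at about $150, a gap of about $9,850 before adjusting for size. Assume other costs are equal and a threshold of $50,000 to $150,000 per QALY. Offsetting the gap then takes 9,850/150,000 = 0.066 to 9,850/50,000 = 0.197 QALY, or roughly 9 to 28 excess deaths in one arm at 0.0069 each. This is a fair argument about the decision, although unequal complication costs would change it. It does not make the reported QALYs or each arm's own ratio correct.

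The baseline part is about precision only, and counting deaths can use up the gain. At r = 0.2 and 5% mortality the net SE is 0.0405 against 0.0366 as planned. This too stands. At 1% mortality and r = 0.2 the adjusted SE of 0.0343 gives √(0.0343² + 0.0098²) = 0.036, about the same as planned.

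Smaller points also have merit. If deaths fall among those lost to follow-up, the denominator is nearer 253/2 = 126.5 and the per-death figure is 0.7/126.5 = 0.0055. The plan converts HerQLes as well as EQ-5D to utilities. It gives no rule for missing utilities in the QALY. A straight line from the preoperative value to 4 weeks may describe early recovery poorly, but the weight involved is small.

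The general sensitivity analyses could include survival, but nothing commits them to it.

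**Conclusion.** The concern holds. As written, time after any death is valued as if lived, and the preoperative EQ-5D plays no part in the QALY. On the assumptions above, each death overstates its arm's mean QALY by about 0.007 (0.002 to 0.013), and mortality of 1% to 5% overstates an arm's own QALY by 0.5% to 2.6%. The incremental error is zero with matched deaths, timing and credited utility, and about 0.007 for each extra death in one arm.

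Baseline adjustment reduces the standard error of the QALY difference by an amount that depends on the between-visit correlation. Counting deaths gives some of that back.

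The issue is confined to Aim 2 and does not touch the primary outcomes or the sample size. It should be corrected because the remedy is cheap, and because the present rule would conceal a survival difference if one occurred. Confidence is medium, since the documents supply no mortality, utility SD or correlation.

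**What to change.** Amend the Specific Aim 2 text as follows.

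1. Replace the all-survive rule with utility 0 from the date of death.
2. Calculate each patient's QALYs as the area under the EQ-5D utility curve from the preoperative value through 4 weeks, 6, 12 and 24 months. State what role, if any, HerQLes-derived utilities keep, and how missing utilities are handled.
3. Estimate the arm difference by regression on arm and baseline utility, and use that estimate as the QALY input to the decision model.
4. Keep the all-survive calculation as a named sensitivity analysis.

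The cost is SAP wording plus one check on data. The preoperative EQ-5D is already collected. The postoperative items under Study Procedures run to "length of hospital stay, discharge date, time to return of bowel function and any readmission" but name neither death nor vital status. The case report forms are not shown, so the sponsor should confirm that date of death is recorded. The Power Calculation allows for attrition without separating deaths from other losses: "Assuming a maximum 20% loss to follow-up, 202 patients will remain in the study sample". Some of those lost could be unrecorded deaths. If dates of death are not recorded, vital status must be ascertained.

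The statistical downside, if mesh does not affect survival, is added chance variation in the QALY difference with SE of about 0.010 to 0.021 at 1% to 5% mortality.
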